1.2.2 Methods

To describe findings during follow up, we will use cumulative incidence curves that reflect the competing risk setting. The follow-up time will be computed in months.

In competing risk survival analysis, the hazard and cumulative incidence of competing (i.e. mutually exclusive) events are estimated over time. The basic competing risk outcome levels reflect the overall study outcome, and are 'surgery performed', 'cyst spontaneously resolved', and 'patient died (for any reason)', whichever comes first. When surgery is performed, this can be further subdivided based on reason for surgery and findings at surgery. For these subdivisions, it is possible that two events (i.e. reasons or findings) occur simultaneously. For example, a patient can undergo surgery due to acute pain and fertility concerns. We therefore specified a hierarchy of the competing events and if two events occur simultaneously, the event highest in the hierarchy is given to the observation. The hierarchies are shown in Box 1. For example, when the patient is operated due to acute pain and fertility concerns, the patient is said to have the event acute pain.

Box 1. Hierarchy of reasons for surgery and findings at surgery.

Reasons for surgery	Findings at surgery
1. Suspicion of malignancy ^a	1. Invasive
2. Pain ^b	2. Borderline
3. Patient request/opportunistic ^c	3. Torsion
	4. Cyst rupture
	5. Minor complications ^d
	6. No complications of tumor

^a Includes ‘suspicion of malignancy based on ultrasound; suspicion of malignancy based on: increase in size, change in morphology, change in vascularity, raised or increase in CA125, raised HE4, CT finding, MRI findings’

^b Includes ‘acute pain (suspected torsion, suspected cyst rupture), chronic pain’

^c Includes ‘fertility concerns, patient request, opportunistic removal’

^d Includes ‘tumor bleeding, adhesions, inflammation/infection’

We will derive cumulative incidence functions for study outcome, reason for surgery, and findings at surgery. For each outcome, figures depicting the cumulative incidence will be produced, as well as tables at time points 12 and 24 months containing the cumulative incidences of the competing events with 95% CI.

Median follow-up will be estimated by the reverse Kaplan-Meier method, i.e. where censoring is denoted as the event, and events denoted as censoring. This is the common method to visualize the censoring function.

Subgroup analyses will also be performed in the same manner as the overall analysis. Subgroup variables are tumour type (unilocular, unilocular-solid, multilocular, multilocular-solid, solid), presumed diagnosis (see table below), subjective assessment (certainly benign, probably benign), Lesion size (median split method + description on the cumulative incidence at cut-offs 3, 4, 5, 7, 10 cm), and menopausal status. For menopausal status, the data collection software contains a bug such that this information is overwritten by the menopausal status of the last visit. Therefore, for a small group of patients who are labeled postmenopausal, it is possible that they were premenopausal at the first visit in the study. However, we will use the variable as currently available in the dataset. If menopausal status is uncertain, we will classify it as postmenopausal if age at inclusion is 50 or higher.

In all subgroup analyses, we will report cumulative incidences on: spontaneous resolution, death (any cause), surgery (any reason), malignancy, torsion, rupture.

In the subgroup analyses, cumulative incidences will only be reported at 24 months.

Table. Presumed diagnoses at first visit

Presumed diagnosis	N (%)
Simple cyst / para-ovarian or salpingeal cyst/ Serous cystadenoma / serous cystadenofibroma	1470 (47%)
Endometrioma	609 (19%)
Teratoma	325 (10%)
Functional cyst	186 (6%)
Fibroma / fibrothecoma	180 (6%)
Mucinous cystadenoma / mucinous cystadenofibroma	129 (4%)
Hydrosalpinx	122 (4%)

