The general aim of this study is the development of the optimal algorithm for the management of all adnexal masses. This can be broken down into different specific objectives: 1) to study the occurrence of complications such as rupture, torsion, or malignancy in patients with benign looking conservatively treated masses; 2) to test the published IOTA diagnostic models for predicting that a mass is malignant at first visit or benign (either on the basis of histology following surgery or by the absence of malignant features on an ultrasound scan one year after the initial visit), and to predict complications (e.g. ocurrence of malignancy and other) during long-term follow-up; 3) to investigate factors that may be related to the need for surgery during long-term follow up; 4) to study the natural history of conservatively treated benign looking masses and to establish descriptive curves of the longitudinal changes seen in parameters from conservatively managed benign tumors (e.g. change in diameter, size of any solid component, number of papillations, or color score). We hope these curves will allow us to determine if any particular growth pattern is associated with complications or malignancy

Related to these four objectives, we aim to carry out the following analyses: 1) descriptive analysis of complications overall and by participating center (anonymised) and overall Kaplan-Meier curves for the need for surgery among benign looking masses; 2) estimation of discriminatory ability of LR1 for malignancy at the initial visit using the c-index and ROC curves and for complications during long-term follow-up using the hazard ratio and c-index within the context of survival analysis; 3) survival analysis to investigate predictors of the need for surgery during long-term follow-up of non-operated masses; 4) the development of longitudinal curves of the changes seen in the characteristics of non-operated masses using longitudinal analysis techniques such as mixed models and functional linear discriminant analysis (FLDA).

Methods

Study design

International multicenter prospective observational cohort study

Eligible for inclusion

- Any woman at least 18 years old with an adnexal mass.
- Any mass with benign ultrasound morphology may be suitable for conservative management.
- Pregnant patients can be included, but their data will be analysed separately.

Exclusion Criteria

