 - o Conservative management with follow up as specified in the protocol
 - o Surgery by a gynaecologist or general surgeon
 - o Surgery by an oncological surgeon

Current status of the patient (this new tab should come before the tab "Histology"). A fixed query could be made to automatically ask the investigator about the status of all patients that were not rescanned 55 weeks after their previous scan as soon as the investigator opens the IOTA 5 study screen.

- Lost to follow up (no other pop-up)
- > Patient stopped participating to the study (please specify why :) (no other pop-up)
- Patient withdrew her consent (data cannot be used for statistical analysis and no reason is aked) (no other pop-up)
- Surgery performed (pop-up of fields about operation below)

If Surgery

- Date of operation:
- Type of operation: cystectomy or oophorectomy or staging etc
 - \circ Laparotomy with vertical incision
 - Laparotomy with horizontal incision
 - o Operative laparoscopy
 - o Diagnostic laparoscopy
 - Primary chemotherapy

- Indication for operation (more than one possibility may be thicked)
 - o Suspicion of malignancy based on ultrasound
 - o Suspicion of malignancy based on other information if so what?
 - Malignancy cannot be excluded
 - Acute pain
 - Chronic pain
 - o Suspected torsion
 - o Fertility concerns
 - o Patient request
 - Increase in size of the tumour
 - Change in morphology of the tumour
 - Increase in CA 125 level
 - Indicated by other imaging technique (CT, MRI...)
 - o Other doctor recommended operation. Please specify the reason: ...
 - o "en passent" removal of the mass when patient was operated for another indication
 - Other: Specify:
- Findings at operation (more than one option may be ticked)
 - No complications of the tumour
 - \circ Torsion
 - o Rupture
 - o Inflammation/Infection
 - Adhesions
 - o Bleeding from tumour
 - o Metastatic cancer
 - Other complications of tumour: specify:
 - $\circ~$ Other non-gynaecological pathology (e.g. appendicitis): specify:
- Complications during operation (within one week of surgery). (more than one option may be ticked) :
 - Conversion from laparoscopy to laparotomy
 - o Bowel perforation
 - o Bleeding requiring transfusion
 - o Embolism, deep venous thrombosis
 - Wound Infection
 - Peritonitis
 - Other: Specify:
- Histological diagnosis (pop up list as before) with open text area ("Details")

If follow up examination:

- Complications of adnexal mass: no /yes

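### Box 1 credits each operation with only its top-ranked reason and finding, so the incidences labelled pain, torsion and rupture may understate how often these occurred

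*SAP*

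**What the plan says.** SAP follow-up study, section 1.2.2, treats surgery, spontaneous resolution and death as competing events and subdivides surgery by reason and by finding. It accepts that within these subdivisions "it is possible that two events (i.e. reasons or findings) occur simultaneously", and settles the matter by rank: "the event highest in the hierarchy is given to the observation".

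Box 1 gives the ranks.

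- Reasons: suspicion of malignancy is first, pain second, patient request or opportunistic removal third. The footnote to the first category takes in suspicion based on "increase in size, change in morphology, change in vascularity", markers, CT and MRI. The footnote to the second covers "acute pain (suspected torsion, suspected cyst rupture), chronic pain".
- Findings: invasive and borderline tumours hold the first two ranks and torsion the third. Rupture follows as "4. Cyst rupture", ahead of minor and no complications.

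The main tables are described as "containing the cumulative incidences of the competing events with 95% CI" at 12 and 24 months. Section 1.2.3 repeats the same rows for all patients, for new masses and for both sensitivity analyses. The 24-month subgroup table carries torsion and rupture but not pain.

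The protocol's surgery form records both items as multi-select. The indication item reads "Indication for operation (more than one possibility may be thicked", and the findings item likewise allows several ticks. The first protocol objective is "to study the occurrence of complications such as rupture, torsion, or malignancy" in conservatively treated masses.

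**The concern.** The database will hold every reason and finding, but the planned cumulative incidences use one per operation. A torsion in a borderline tumour goes into the borderline row. A rupture found with torsion goes into the torsion row. An operation for pain and for suspicion of malignancy goes into the suspicion row. The table rows are then labelled simply as pain, torsion and cyst rupture, and the pain footnote does not say that women who also had a suspicion reason have been removed.

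The objective asks how often torsion and rupture occur, not how often they occur without a higher-ranked finding. A reader advising a woman with a benign-looking mass is likely to take the row as the former. The 95% CI offers no protection, because it reflects sampling error around the Box 1 category and not the gap between the two definitions. The size of the loss could also differ between subgroups if overlap does.

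**Working it through.** The plan states no event count, incidence or overlap rate for this point, so there is no planned figure to reproduce. The check is of the rule and its algebra, followed by an assumed range.

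**1. The rule.** Coding Box 1 as keeping the best rank reproduces the SAP's own example: acute pain with fertility concerns is counted as pain. Applied to other pairs:

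| Recorded together | Counted as | Row that loses the case |
|---|---|---|
| Suspicion of malignancy + pain | Suspicion | Pain |
| Borderline + torsion | Borderline | Torsion |
| Invasive + rupture | Invasive | Rupture |
| Torsion + rupture | Torsion | Rupture |

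Torsion can be displaced only by invasive or borderline histology, and rupture only by those or by torsion. Malignancy as a whole cannot be displaced by any lower-ranked finding.

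**2. The identity.** All labels of one operation share one event time, and relabelling an operation leaves all-cause event-free survival unchanged. The Aalen-Johansen increments therefore add, and for any item at time t:

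CIF(Box 1) = CIF(any occurrence) − CIF(item together with a higher-ranked item)

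The planned figure is thus never above the any-occurrence figure, and it equals it when there is no overlap. If q is the share of such operations that also carry a higher-ranked label, then approximately:

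CIF(any occurrence) = CIF(Box 1) / (1 − q)

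**3. Numerical check.** Data were simulated for 2,000 patients with assumed monthly hazards (resolution 0.010, death 0.0005, suspicion without pain 0.002, any pain 0.003, request 0.003) and censoring uniform between 10 and 30 months. Each q used a separate random draw.

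| Nominal q | Any occurrence, 24 months | Box 1 coding | Overlap incidence |
|---|---|---|---|
| 0 | 5.66% | 5.66% | 0 |
| 10% | 5.02% | 4.38% | 0.64% |
| 20% | 5.80% | 4.82% | 0.98% |
| 30% | 6.24% | 4.55% | 1.69% |
| 50% | 4.73% | 2.46% | 2.27% |

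In every row the second figure plus the fourth equals the first.

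**4. Range over q (assumed; not in the documents).** For a true any-occurrence incidence of 5.0%, the table would show 5.0% × (1 − q):

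| q | Reported | True / reported |
|---|---|---|
| 0 | 5.0% | 1.00 |
| 10% | 4.5% | 1.11 |
| 20% | 4.0% | 1.25 |
| 30% | 3.5% | 1.43 |
| 50% | 2.5% | 2.00 |

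**5. Pain, seen from the suspicion row.** Assume 24-month incidences of 6.0% for suspicion and 4.0% for pain as Box 1 would report them, and let p be the share of suspicion operations that also had pain. Surgery with pain is then 4.0% + p × 6.0%.

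- p = 0: 4.0%, no shortfall.
- p = 5%: 4.0% + 0.3% = 4.3%; shortfall 1 − 4.0/4.3 = 7%.
- p = 20%: 4.0% + 1.2% = 5.2%; shortfall 1 − 4.0/5.2 = 23%.

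All inputs to this step are assumptions.

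**The case against.** The best defence is that this is a disclosed choice of estimand. The SAP says items can coincide, explains that competing events must be mutually exclusive, fixes the order in advance and gives an example. As estimates of the Box 1 categories, the figures are correct. That stands, and it is why the hierarchy should remain for the curves. It does not answer the point about row labels, or the absence of any any-occurrence estimate.

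Second, the loss for torsion and rupture is probably small. SAP section 1.1 restricts the cohort to masses judged certainly or probably benign, so torsion in a malignant tumour should be uncommon. This stands as a judgement; no overlap figure supports or contradicts it.

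Third, two planned tables soften the loss. One lists every confirmed malignancy, rupture or torsion with its finding or findings and its time in follow-up, so coincident torsion and rupture should be visible case by case. It gives no cumulative incidence or CI and does not cover pain. The other counts individual reasons for surgery among new masses, but does not say whether one patient can count in several rows.

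Fourth, pain is the outcome with the most room for overlap but the weakest link to the first objective, which names rupture, torsion and malignancy. A reason for surgery is an indication, and pain as a complication is recorded separately at follow-up visits. This too stands: an any-occurrence row would describe surgery with pain, not the risk of pain.

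Fifth, a reader might infer that any pain case with a growing cyst is counted as suspicion. The protocol form lists growth as its own indication, whereas the Box 1 footnote speaks of suspicion based on growth. How the one maps to the other is unclear, so that reading is possible but not established.

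**Conclusion.** The point holds in conditional form. The incidences labelled pain, torsion and cyst rupture estimate each item without any higher-ranked item, and may understate how often it occurred. The direction follows from the rule, and the size equals an overlap that the documents do not report.

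A reader might go further and conclude that the three incidences are undercounted as a matter of fact, or that about a quarter of pain surgery is lost. The documents support neither. With no overlap the loss is zero, and the 7% and 23% above follow entirely from assumed incidences and overlap shares. For torsion and rupture the effect is probably small in a cohort assessed as benign. For surgery with pain it may be larger, because the category above it is broad.

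This is a reporting improvement of low severity, not an error in the competing-risks analysis.

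**What to change.** 1. Keep Box 1 for the mutually exclusive cumulative incidence curves and their rows.
2. In the 12- and 24-month tables, add any-occurrence cumulative incidences with 95% CI for surgery with pain, torsion and rupture. For each, the event is surgery with that item recorded; the competing events are surgery without it, resolution and death.
3. Use the same definition for torsion and rupture in the 24-month subgroup table.
4. Footnote that the added rows overlap and do not sum to total surgery.
5. State whether the table of reasons for surgery counts a patient under every reason recorded or only one.

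No extra row is needed for malignancy, since invasive and borderline already hold the top two ranks.

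The cost is negligible: the same estimator applied to fields the form already collects, a few extra rows and a footnote. Comparing the added rows with the Box 1 rows would also reveal the overlap that is unknown now.

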- If yes : date of first complication:

- And pop up list (you can select more than one):
 - Acute pain
 - \circ Chronic pain
 - Suspected torsion
 - o Infection
 - Haemorrhage
 - o Rupture
 - $\circ~$ Other, please specify:
- Death: date
- Death directly or indirectly relatd to adnexal mass?
- cause of death (

• Autopsy findings: specify:

Not needed for IOTA phase 5: second stage tests

Consent / information leaflet

Information leaflets are at the discretion of the participating centres. Approval of the local Ethical Committee for clinical studies is necessary.

Serum tumour markers

Serum CA 125 measurements or other tumour markers are performed locally, using a CA 125 II immunoradiometric assay

Tissue collection

Preferably the whole tumour should be removed. However, representative biopsies may be sufficient (e.g. in advanced ovarian cancer or endometrioma).

Tumour classification

Tumours are classified according to the criteria recommended by the International Federation of Gynecology and Obstetrics (FIGO). In malignant tumours the degree of differentiation is included.

Statistical analysis

For the first objective, a descriptive analysis of complications on all data and stratified for participating center (anonymized) will be performed, as well as an overall Kaplan-Meier curve of 'complication free survival'. Complication free survival is defined as the time to the need for surgery during long-term follow-up. Patients that did not need surgery at the end of the follow-up period are right censored at the time of the last examination.

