Figure: Histogram of time of follow up scans (all follow up scans, i.e. not only the last scan per patient). This will be done once based on data from all patients, and once based on data from patients with newly detected masses only.

Figure: Cumulative incidence curve for study outcome (died, resolution, surgery). This will be done once based on data from all patients, and once based on data from patients with newly detected masses only.

Figure: Cumulative incidence curves for reason for surgery (study outcome surgery is subdivided into different reasons as specified above in Box 1; only curves for these reasons are given, not for other study outcomes (died/resolved)). This will be done once based on data from all patients, and once based on data from patients with newly detected masses only.

Figure: Cumulative incidence curves for surgery outcome (study outcome is again subdivided, but now in terms of findings at surgery as specified above in Box 1). Panel A gives all events with y-axis from 0 to 1; Panel B given zoomed in plot focusing only on malignancy, torsion, rupture. This will be done once based on data from all patients, and once based on data from patients with newly detected masses only.

Table: Cumulative incidence of study outcomes, reasons for surgery, and findings at surgery at 12 and 24 months with 95% CI; Table containing the following statistics at time points 12 months and 24 months: cumulative incidence with standard error and 95% CI. This will be done once based on data from all patients, and once based on data from patients with newly detected masses only.

	12 months	24 months
Study outcome		
Cyst resolution		
Patient died		
Surgery performed		
Reason for surgery		
Suspicion of malignancy		
Pain ^b		
Patient request/opportunistic ^c		
Findings at surgery		
Invasive		
Borderline		
Torsion		
Cyst rupture		
Minor complications		
No complications		

Table: Table of all cases with confirmed malignancy, rupture, or torsion, with descriptive information. *The exact list of parameters to be described should still be defined.*

Case	New or known mass at inclusion	Time in follow up before surgery	Finding(s) at surgery	Age at inclusion	Lesion size at first scan	Change in lesion size	...
1							
2							
3							
4							
5							
6							
7							
...							

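### The follow-up SAP counts complications of conservatively managed masses only when they are found at surgery, so those recorded without an operation, and mass-related deaths, appear in no planned output

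*SAP*

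**What the plan says.** In the follow-up SAP, section 1.2.2, the basic competing-risk levels "are 'surgery performed', 'cyst spontaneously resolved', and 'patient died (for any reason)', whichever comes first". Complications enter one level down: "When surgery is performed, this can be further subdivided based on reason for surgery and findings at surgery". Box 1 places invasive tumour, borderline tumour, torsion, cyst rupture and minor complications (bleeding, adhesions, inflammation or infection) in its column of findings at surgery. The planned curves follow from that: "We will derive cumulative incidence functions for study outcome, reason for surgery, and findings at surgery". Section 1.2.3 describes the figure that zooms in on malignancy, torsion and rupture in the same terms: "study outcome is again subdivided, but now in terms of findings at surgery as specified above in Box 1". For subgroups, section 1.2.2 says: "In all subgroup analyses, we will report cumulative incidences on: spontaneous resolution, death (any cause), surgery (any reason), malignancy, torsion, rupture".

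The protocol's first objective is "to study the occurrence of complications such as rupture, torsion, or malignancy in patients with benign looking conservatively treated masses". Its Statistical analysis section promises, for that objective, a description of complications on all data and by centre, plus a Kaplan-Meier curve of complication-free survival. The study screen asks at each follow-up examination whether the mass has caused a complication. It continues "If yes : date of first complication", followed by a multiple-choice list: acute pain, chronic pain, suspected torsion, infection, haemorrhage, rupture, other. It also asks "Death directly or indirectly relatd to adnexal mass", with cause of death and autopsy findings.

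**The concern.** The women whose safety is in question are those not operated on at the outset, and some complications in that group need never lead to an operation. The protocol foresaw this and gave such events their own dated fields, separate from the surgery block. The follow-up SAP gives no rule for these fields and lists no output from them, although section 1.2.1 says the all-patient analysis is meant to give a full account of what the study found.

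Objective 1 is therefore answered only for complications that reached an operating theatre. The 12- and 24-month figures are the interim evidence on conservative management. A reader who takes surgically found events for the total would understate the risk by an unknown amount. In the subgroup table, where the columns read simply malignancy, torsion and rupture, nothing in the headings warns against that reading.

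**Working it through.** The plan states no figure that depends on this definition, so there is nothing to reproduce. The check is a trace of recorded fields to planned outputs, followed by an illustration of scale.

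**1. Where each recorded event goes** (protocol study screen against follow-up SAP 1.2.2)

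| Recorded | Counted as |
|---|---|
| Any Box 1 finding at an operation | Finding at surgery |
| Rupture, no operation, cyst later gone | Spontaneous resolution only |
| Infection or haemorrhage, no operation, mass persists | No event; at risk until a later event or censoring |
| Suspected torsion, no operation | No event; suspected torsion appears only as a reason for surgery, under pain |
| Death related to the mass, no operation | Death from any cause only |

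**2. Whether any output escapes this.** I went through section 1.2.3: the outcome rows of the characteristics table, the cumulative incidence figures, the 12/24-month table, the case listing (its columns give time before surgery and findings at surgery), the subgroup table and both sensitivity tables. None draws on the follow-up complication fields or on relation of death to the mass.

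**3. Strength by outcome**
- Rupture, infection, haemorrhage: each is a choice on the follow-up list. Strong.
- Torsion: only the suspected form is on that list. Weaker.
- Malignancy: not on the list. Without surgery it would show mainly through cause of death or autopsy. The study screen also lists primary chemotherapy under type of operation, so some cancers without resection may already enter the surgery branch. Weaker still.

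**4. Scale, by illustration.** The SAP's table of presumed diagnoses gives seven counts with rounded percentages. The tightest limits on the total are 609/0.195 = 3,123.1 from below and 1470/0.465 = 3,161.3 from above, so N lies between 3,124 and 3,161. Ten complications without surgery are then 10/3,161 = 0.316% to 10/3,124 = 0.320%, about 0.32 percentage points as a crude proportion.

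For rupture hidden in resolution, the share missed is (24-month resolution) × (share of resolutions with a recorded rupture). Neither rate is in the documents. Assuming 10% to 30% and 1% to 5%, it runs from 0.10 × 0.01 = 0.10 to 0.30 × 0.05 = 1.50 percentage points.

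A simulation with constant hazards assumed 24-month incidences of about 19.5% resolution and 14.6% surgery, with 2% of operations showing the complication. Surgery alone gives 14.6% × 2% = about 0.3%. Suppose 1% to 5% of resolutions carry a recorded rupture, and the 24-month risk of a complication without surgery in a persisting mass is 0.1% to 0.5%. The total then becomes 0.58% to 1.67%, about 1.9 to 5.6 times as high. This shows that rare outcomes are sensitive to the definition. It is not an estimate for this study.

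**The case against.** Restricting to surgical confirmation looks deliberate. Section 1.2.1 of the follow-up SAP speaks of confirmed complications, and the case listing in 1.2.3 covers confirmed cases. The protocol itself defines complication-free survival as time to need for surgery. Against that narrower target the estimates are not biased, so a reader who infers that the malignancy, torsion and rupture rates are shown to be biased downwards goes further than the documents allow. This stands, but the SAP never states the narrower target, and the protocol's descriptive analysis of complications is a separate commitment alongside the surgery-based curve.

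A reader might also infer that the restriction is concealed. It is not, in the main outputs: the 12/24-month table and both sensitivity tables carry a findings-at-surgery block. Only the subgroup table lacks the qualifier.

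Nor is resolution shown to be inflated. A ruptured cyst that is later absent has disappeared without surgery, which fits the SAP's event as named. What is lost is the knowledge that some resolutions followed a complication.

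Finally, the data remain in the database. The plan is an interim one, and nothing in it withdraws the protocol's descriptive analysis or its yearly review of acute complications. That is fair, but neither is listed in this SAP.

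**Conclusion.** The follow-up SAP answers objective 1 only for complications found at an operation and leaves unused the fields the protocol provides for the rest. This is firm for rupture, infection and haemorrhage. It is limited for torsion, and for malignancy it rests mainly on cause of death and autopsy.

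The direction is clear: leaving out recorded events can only lower a total complication incidence. The size cannot be derived, because the documents give no rate of complications without surgery and do not show how completely those fields were filled. The figures above rest on assumed rates, except the conversion of 10 events to about 0.32 percentage points. That one assumes the presumed-diagnosis table describes the analysed cohort; among new masses alone the denominator is smaller and each event weighs more.

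The planned outputs remain usable for what they measure. The change is worth making because it decides what the interim analysis can conclude about conservative management.

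**What to change.** Keep the surgery-confirmed outcomes, state in 1.2.2 that this is what they are, and label the subgroup columns in 1.2.2 and 1.2.3 as found at surgery, in line with the 12/24-month tables. Then add, for all masses and for new masses:

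- (a) The 12- and 24-month cumulative incidence of a first complication, either recorded at follow-up (dated by the first-complication field, with pain-only entries shown separately) or found at surgery. Surgery without complication, resolution and death are the competing events. State that a rupture followed by disappearance of the cyst counts here as a complication.
- (b) Counts by type of complications without surgery: rupture, suspected torsion, infection, haemorrhage. Use counts rather than separate dated curves, because the form holds one date for several ticked types.
- (c) The number of women classed as spontaneously resolved who had an earlier recorded rupture or haemorrhage.
- (d) Deaths split by relation to the mass, with any cancer identified from cause of death or autopsy.

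The cost is some extra rows and one further curve, from fields already on the study screen. The downside is that these events are clinically recorded rather than surgically confirmed, and completeness may vary by centre: section 1.1 of the follow-up SAP already reports marked heterogeneity in adherence to follow-up. They should therefore stay in rows of their own.
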